Study Title: Use versus non-use of bladder catheterization in uncomplicated cesarean delivery

PI: [name]

Version 1.0 - January 23, 2024

Research Protocol

Medical Centre that focuses on sound methodology and clear outcomes to build on the existing evidence on this topic.

Primary Research Question

To investigate the impact of routine bladder catheterization in uncomplicated CS on hospitalization time (readiness to discharge), time to ambulation, urinary retention, development of UTI, prevention of bladder injury, operating time, and patient satisfaction.

Study Design

This would be a randomized controlled trial conducted on the labour and delivery and post-partum unit at a large academic site (Foothills Medical Centre) in Calgary, Alberta. Study recruitment of patients awaiting delivery via CS would occur either in participating prenatal clinics in Calgary or in obstetrical triage by a trained nurse research assistant. Participants would be randomized into either a catheterized or non-catheterized group prior to their scheduled elective CS. Allocation concealment will be ensured by using either a central computer generator for randomization if funding permits, otherwise sealed, opaque, and sequenced envelopes will be used. Since we anticipate potential differences in patients with increasing parity, randomization will be stratified by parity and blocked to prevent imbalance in treatment groups.

Patients placed in the catheterized group will have an indwelling catheter placed after anesthetic has been administered. It would be removed at 12 hours post CS by postpartum nursing staff. Participants in the non-catheterized group would be encouraged to empty their bladders just prior to transfer to the operating room where they will undergo surgery without an indwelling catheter. If there is an intraoperative decision to place an indwelling catheter, the reason for doing so will be recorded on the post-operative survey described below. Due to the nature of this study design, blinding of either party is not feasible. Inclusion criteria are women who are 18 years of age or older with a singleton pregnancy presenting for an elective primary or repeat CS. Exclusion criteria include diagnosis of abnormal placentation including placenta previa, vasa previa, or suspected invasive disease.

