The primary outcomes are hospitalization time, time to ambulation, urinary retention, development of UTI, prevention of bladder injury, and patient satisfaction. For many of these baseline estimates for a sample size calculation are not available. However, based on data from FMC the average length of stay post CS is 2.1 days. Converting this to hours and assuming a power of 80% and setting alpha at .05 a sample 30 subjects would provide 80% power to detect a 50% difference in length of stay. A sample of 128 would have adequate power to detect a difference in LOS of 25%. We aim to recruit 140 individuals. Currently FMC performs between 62-100 elective CS per month (2022-march 23 data). Therefore, with even a modest recruitment rate we should easily recruit sufficient patients. Time to discharge, time to ambulation and patient satisfaction (VAR) will be analysed with a comparison of means after appropriate transformations. A t-test will be used to assess statistical significance. Bivariate data such as urinary retention, UTI and bladder injury will be described as rates and statistical significance assessed with a Fisher's exact test.

Risks and Benefits

The benefits of the proposed study are the gathering of information that could help guide clinical practice with regards to the use of bladder catheterization in uncomplicated cesarean delivery. While evidence exists, there are significant issues with methodology that make the results difficult to interpret. Based on previous literature, the largest risk to participants is the need for intraoperative catheterization based on the surgeon's discretion after abdominal entry. Precaution to maintain a sterile environment in this case would be taken.

Ethics ID: REB24-0044

Study Title: Use versus non-use of bladder catheterization in uncomplicated cesarean delivery

PI: [name]

Version 1.0 - January 23, 2024

Research Protocol

References

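### Urinary retention and UTI are tested with Fisher's exact test, which is valid but conservative at this trial size; prespecifying Boschloo's exact test would recover some power at almost no cost.

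*Combined protocol and SAP*

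**What the plan says.** The Statistical Analysis section gives one sentence to the analysis of the binary outcomes: "Bivariate data such as urinary retention, UTI and bladder injury will be described as rates and statistical significance assessed with a Fisher's exact test". It does not state sidedness, and it promises no effect estimate or interval beyond the rates.

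The only significance level in the document stands inside the length-of-stay calculation: "setting alpha at .05 a sample 30 subjects would provide 80% power to detect a 50% difference in length of stay". No level, target difference or power is given for retention or UTI. Of its outcomes in general the section says: "For many of these baseline estimates for a sample size calculation are not available".

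The size is a total: "We aim to recruit 140 individuals". Study Design describes two groups ("Participants would be randomized into either a catheterized or non-catheterized group prior to their scheduled elective CS") but gives no allocation ratio.

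Both outcomes belong to the Primary Research Question, which lists "time to ambulation, urinary retention, development of UTI, prevention of bladder injury, operating time, and patient satisfaction" after hospitalization time. Study Design calls them secondary, whereas Statistical Analysis lists them among the primary outcomes.

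**The concern.** Fisher's test conditions on the total number of events. With fixed arm sizes and few events, only a handful of tables are possible for each total, so the p-value moves in large steps and the real false-positive rate falls well below the nominal level. Power falls with it.

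UTI is the benefit that the Background stresses most, and it is counted only when it needs antibiotics within four weeks of delivery, so it may well be infrequent. Retention may be infrequent too. In 140 women, a difference that an equally valid exact test would call significant could be reported as non-significant because of the test chosen.

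**Working it through.** **Plan's own figure.** There is none to reproduce: the stated sample sizes (30, 128 and the target of 140) concern length of stay.

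**Inputs.** From the plan: Fisher's test and a total of 140. Assumed: 1:1 allocation, no loss (so 70 per arm), two-sided testing at 5%, and all event rates.

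**Step 1: why Fisher is conservative here.** Suppose five events occur in total, all in one arm. The one-sided probability given the total is (70 × 69 × 68 × 67 × 66) / (140 × 139 × 138 × 137 × 136) = 0.0290, so the two-sided p is 2 × 0.0290 = 0.058. With five events or fewer, Fisher's test therefore cannot reach 5% however they fall. With six, 6 v 0 gives p = 0.028.

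**Step 2: true size.** Let *a* and *b* be the event counts in the two arms, and R the set of the 71 × 71 possible tables that a test rejects. At a common event rate *p*,

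size(*p*) = Σ over R of C(70,*a*) C(70,*b*) *p*^(*a*+*b*) (1−*p*)^(140−*a*−*b*).

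For Fisher, R is every table with two-sided Fisher p ≤ 0.05. Boschloo's test uses the Fisher p as its statistic and takes the largest cut-off that keeps size(*p*) at or below 5% for every *p*. Here the cut-off is 0.0626. Because it exceeds 0.05, every table that Fisher rejects is also rejected by Boschloo, so Boschloo cannot be less powerful.

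| Common event rate | Fisher size | Boschloo size |
|---|---|---|
| 1% | 0.01% | 0.07% |
| 3% | 0.5% | 1.7% |
| 5% | 1.4% | 3.1% |
| 10% | 2.5% | 3.6% |
| 30% | 3.3% | 4.2% |
| 50% | 3.4% | 4.9% |
| Maximum at any rate | 3.4% | 4.9% |

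Fisher's size first reaches 1% at an event rate of 4.1%.

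**Step 3: power.** Power = Σ over R of Bin(*a*; 70, *p*1) × Bin(*b*; 70, *p*2).

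| Rates | Fisher | Boschloo | Gain (points) |
|---|---|---|---|
| 10% v 1% | 51.5% | 64.6% | 13.1 |
| 10% v 2% | 36.2% | 47.5% | 11.2 |
| 15% v 3% | 62.4% | 69.1% | 6.7 |
| 15% v 5% | 40.7% | 46.2% | 5.6 |
| 20% v 5% | 72.2% | 76.0% | 3.8 |
| 25% v 10% | 58.4% | 61.3% | 2.9 |
| 30% v 10% | 81.3% | 83.1% | 1.8 |
| 40% v 20% | 68.3% | 71.9% | 3.6 |
| 50% v 30% | 61.4% | 67.2% | 5.8 |

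Gains are taken before rounding. Over a grid of rates, keeping scenarios where Fisher's power is 20% to 85%, the gain by the lower arm's rate is:

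- 1% to 5%: 2.7 to 14.0 points (median 6.6)
- 6% to 10%: 1.6 to 4.8 points (median 3.2)
- 11% to 30%: 1.8 to 5.9 points (median 3.6)

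Outside that grid, with no events possible in one arm, the largest gain found was 18 points (7% v 0%: 37% to 55%).

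**Step 4: tables where the choice decides the result.** With 70 per arm: 9 v 2 events gives Fisher p = 0.055 and Boschloo p = 0.038; 5 v 0 gives 0.058 and 0.041; 7 v 1 gives 0.063 and 0.049, the last only just inside 5%.

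**Step 5: sensitivity to arm size.** At 64 per arm (the plan's 128) Fisher's maximum size is 3.5%. Power goes from 31% to 43% for 10% v 2%, and from 36% to 42% for 15% v 5%.

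**The case against.** The strongest reply is that nothing here is wrong. Fisher's test is conventional and controls type I error. Alpha is an upper limit, not a promised rate, and a size below 5% respects it. That stands. A reader might infer that the trial runs at 1% to 3% in breach of a stated 5%. The documents do not support this, since alpha appears only in the length-of-stay calculation and Fisher's test honours it as a bound.

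A second reply is that the size of the gain depends on rates the plan does not supply. That stands too. A reader might infer a general loss of 5 to 15 points. In the grid of lower rates from 1% to 30%, only 14% of scenarios fall in that band, and they lie mostly where one arm's rate is 5% or less.

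Third, changing the test does not rescue these outcomes. For 15% v 5%, the usual normal-approximation formula gives [1.96 × √(2 × 0.10 × 0.90) + 0.842 × √(0.15 × 0.85 + 0.05 × 0.95)]² / 0.10² ≈ 140.1, so 141 per arm for 80% power, about twice what is planned. This is correct, but it is a separate gap and no reason to discard power.

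Fourth, Statistical Analysis lists six primary outcomes without a multiplicity adjustment. Error control under Boschloo is per test, and using more of each 5% raises the familywise rate somewhat. That is a fair qualification, but leaving the conservatism of one test to stand in for a multiplicity rule is not a plan.

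Finally, neither test uses the parity strata from the randomization. The proposed change leaves that as it is.

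**Conclusion.** The point holds as a minor efficiency improvement, not as an error. At 70 per arm Fisher's true two-sided size is about 1% to 3.4% for event rates of about 4% or more, and under 1% below that. Boschloo's test has a maximum size of 4.9% and never has less power. Under assumed rates the gain is about 3 to 14 points when one arm's rate is about 5% or less, and about 2 to 6 points otherwise.

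The direction of the gain follows from how the test is built. Its size rests on the assumed rates, 1:1 allocation and no loss; at 64 per arm the conclusion is the same. The point concerns retention and UTI only, not whether bladder injury can usefully be tested. Both outcomes would remain without planned power under either test.

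**What to change.** In Statistical Analysis, name Boschloo's unconditional exact test, two-sided at 5% with the arm sizes as the fixed margins, in place of Fisher's test for urinary retention and UTI. Add that each will be reported as a risk difference with a 95% confidence interval, for example by Newcombe's method.

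State that the test decides significance, because the interval can disagree in borderline tables: 13 v 5 events gives Boschloo p = 0.0515, yet the Newcombe interval runs from 0.002 to 0.228 and excludes zero.

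Make the change before any outcome data are seen. Switching after a table such as 9 v 2 would look like choosing the test by its result.

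The cost is a sentence or two of wording. The test is in standard software and needs no new data, and type I error per test stays at or below 5%. The one small downside is that the test is less familiar to clinical readers.
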